2.2.5 Worst-case

A worst-case analysis visit will be created for parameters for which abnormalities and/or toxicity grades are defined to summarize values considered as the worst-case. For abnormalities it is derived per parameter and in case both the lowest and the highest values are considered abnormal, a patient can have 2 worst-case analysis visits for a same parameter. For toxicity grades the worst-case is the value associated to the highest toxicity grade and is derived per parameter and toxicity direction (hypo / hyper).

All non-missing post-baseline values, including unscheduled assessments will be considered when deriving the worst-case analysis visit.

SGS	Statistical Analysis Plan	
ARGX-113-1801	Final analysis	Final 1.0 of 28MAR2022

2.3 IMPUTATION AND ROUNDING RULES

2.3.1 Missing values

No imputation will be done of missing values (i.e. observed cases analysis) for safety. For imputation on missing values related to efficacy, see appropriate section of the applicable efficacy endpoint.

2.3.2 Values below or above a threshold

Safety values expressed as below (or above) the detection limit will be imputed by the value of the detection limit itself. Listings will always show the non-imputed values.

PK concentrations below the detection limit will be flagged as Below the lower Limit of Quantification (BLQ) in the listings. For descriptive statistics by scheduled timepoint, BLQ values will be set to zero. For Above the upper Limit of Quantification (ALQ) values, all ALQ values will be set to the upper limit of quantification for the descriptive statistics by scheduled timepoint. Listings will always present the original value.

2.3.3 Rounding

Variables will be rounded to the appropriate number of decimals at display level:

- Time since diagnosis and BMI will be rounded to 1 decimal.
- Ratios will be rounded to the number of decimals of the parameter with the least number of decimals.
- Safety laboratory results will be rounded to a maximum of 3 decimals.

2.3.4 *Outliers*

There will be no outlier detection. All measured values will be included in the analyses.

2.4 PRESENTATION OF RESULTS

All descriptive outputs described in this SAP will be repeated by region (Japanese / Non-Japanese as defined in the study protocol) to support the summary document of the J-MAA submission. The definition of a Japanese participant in the protocol is a participant whose parents and 4 grandparents are Japanese, who has the Japanese nationality, was born in Japan, has not lived outside of Japan for a total of >10 years, and currently lives in Japan. Note that these additional outputs will not be included in the submissons to other health authorities.

2.4.1 Calculation of descriptive statistics and percentages

For continuous variables, full descriptive statistics will only be presented if there are at least 2 non-missing observations. Alternatively, only the number of non-missing data points and mean are shown.

Descriptive statistics will include the number of non-missing data points, the arithmetic mean, the standard deviation (SD), the median, minimum, Q1, Q3, and maximum. In addition, for PD, the standard error (SE) will be provided. For efficacy and descriptive tables by analysis visit, the standard error (SE) and 95% CI will be provided in addition.

SGS	Statistical Analysis Plan	
ARGX-113-1801	Final analysis	Final 1.0 of 28MAR2022

Mean, median, Q1 and Q3 will be presented with 1 more decimal place than the individual values. The SD and SE will be presented with 2 more decimal places than the individual values. Minimum and maximum will be presented with the same number of decimal places as the individual values.

Descriptive statistics for PK concentrations and PK parameters will include n (number of observed values), arithmetic mean, SD, median, minimum and maximum, coefficient of variation (CV%), geometric mean and geometric CV%.

Serum concentrations and PK parameters will be reported as received by the bioanalytical laboratory. Descriptive statistics will be presented with 3 significant digits in μ g/mL (where appropriate), except values ≥ 1000 which will be presented without the decimals. If more than half of the values per time point are BLQ, the arithmetic mean will be reported as BLQ and SD, CV%, geometric mean and geometric CV% will not be calculated. If (one or more) BLQ is reported at a time point, the geometric mean and geometric CV% will not be calculated for that time point.

For event-type safety data, the number and percentage of patients with an event will be shown. The denominator will be the number of all patients in the analysis set per treatment and phase.

For frequency tabulations and cross-tabulations, the denominator will be the number of all patients in the analysis set per treatment. For tables where results are shown by analysis visit, the denominator will be the number of all patients in the analysis set per treatment and per analysis visit. Missing values will never be included in the denominator count when computing percentages. For cross-tabulations of postbaseline results versus baseline results, a 'missing' category will be shown for baseline results if applicable.

2.4.2 Presentation of treatments

The following treatment labels will be used in the tables and listings:

- efgartigimod
- placebo

In the general characteristics analysis, a grand total will be added to summarize all patients over treatments. Grand totals will be shown last.

2.4.3 Ordering in tables and listings

All tables will be presented per treatment, unless specified otherwise. In by-visit displays, worst-case will be shown last, if present.

In listings for general characteristics, results will be ordered by treatment and patient, unless specified otherwise.

All other listings will be ordered by treatment, patient, analysis visit, and time point, unless specified otherwise.

In tables showing several parameters, each parameter will begin on a new page and parameters will be sorted alphabetically, within the parameter category if applicable.

The efgartigimod treatment group will always be shown first, then the placebo treatment group.

3. GENERAL CHARACTERISTICS ANALYSES

3.1 PATIENT DISPOSITION

The following patient data will be tabulated:

- The number of patients in each analysis set
- The number and percentage of patients by country and site
- The number and percentage of patients for each analysis visit.
- Descriptive statistics of the phase duration (see section 2.2.1), calculated as phase end date phase start date + 1 day
- The number and percentage of screen failures, of patients randomized but not treated and of patients who completed or discontinued the trial as documented on the study termination page and the number and percentage of patients for each trial discontinuation reason (including reasons for screen failures).
- The number and percentage of patients who completed or discontinued the treatment as documented on the end of treatment page and the number and percentage of patients for each treatment discontinuation reason.
- The number and percentage of patients who roll over to study ARGX-113-1803.

All information collected in the CRF concerning treatment allocation and study and treatment discontinuation will be listed.

3.2 PROTOCOL DEVIATIONS AND ELIGIBILITY

The number and percentage of patients with major and minor protocol deviations will be tabulated, overall and per class of deviation.

All available information concerning major and minor protocol deviations, violations on eligibility criteria, patients not treated and patients excluded from the efficacy analysis will be listed.

3.3 DEMOGRAPHIC AND OTHER BASELINE CHARACTERISTICS

3.3.1 Available data

The following parameters will be available:

• Demographics: sex at birth, age at informed consent, race, ethnicity, height, weight at baseline, year of birth, date of signing ICF.

SGS	Statistical Analysis Plan	
ARGX-113-1801	Final analysis	Final 1.0 of 28MAR2022

• Baseline disease characteristics: date of diagnosis, history of splenectomy (yes versus no), receiving concurrent ITP therapies at baseline (yes vs. no), history of gastrointestinal bleeding (yes versus no + number of times), history of intracranial hemorrhage (yes versus no + number of times), history of hemorrhage for coagulation disorder (yes versus no + number of times), patient with chronic or persistent ITP, received prior ITP therapy (yes versus no), baseline platelet level, baseline SF-36 (v2), baseline PRO: Functional Assessment of Cancer Therapy questionnaire-Th6 (FACT Th6) questionnaire (Total FACT Th6 score) and Functional Assessment of Chronic Illness Therapy (FACIT) fatigue Scale (Total FACIT Fatigue score), WHO-classified bleeding events.

3.3.2 Derivation rules

The following parameters will be derived:

• Body mass index (BMI) at baseline (kg/m²) = (body weight at baseline (kg)) / (height at screening (m))²

Note: The BMI will be recalculated and rounded as detailed in section 2.3.3, even when already available in the database.

- Age category: 18-<65 years; 65-<75 years; ≥ 75 years
- Weight category at baseline: <50 kg, 50-<75 kg, 75-<120 kg, $\ge 120 \text{ kg}$
- Baseline platelet level category: $(<15\times10^9/L \text{ versus} \ge 15\times10^9/L)$
- Ethnicity category: Japanese versus non-Japanese (including Hispanic or Latino, Not Hispanic or Latino, and Not allowed to ask per local regulations)
- Region: country will be categorized into the following regions: United States / Japan / Europe / rest of the world
 - Europe includes EU countries, and EFTA countries (Norway, Iceland, Liechtenstein and Switzerland)
- Time since diagnosis (years): (date of ICF date of initial diagnosis)/365.25. Partially missing dates of diagnosis will be imputed as follows:
 - Missing start day will be imputed with 1
 - Missing start day and month will be imputed with 1JAN
 - Note: Result will be rounded as detailed in section 2.3.3.
- Baseline WHO bleeding score category: No bleeding, Grade 1, ≥ Grade 2, calculated as the maximum bleeding scale over the different body systems available at baseline.
- See section 3.5.2 for categories of type of ITP therapy.
- See section 4.1.2.3 for the definitions of FACT Th6, FACIT and the WHOclassified bleeding events.

SGS	Statistical Analysis Plan	
ARGX-113-1801	Final analysis	Final 1.0 of 28MAR2022

3.3.3 Presentation of results

Demographics will be presented using descriptive statistics for age, height, weight and BMI at baseline, and frequency tabulations for age category, weight category at baseline, sex at birth, race, ethnicity, ethnicity category and region.

Baseline disease characteristics will be presented using descriptive statistics for:

- time since diagnosis
- platelet level
- SF-36 (v2): norm-based P-CS and M-CS scores
- total FACT-Th6 score
- total FACIT-Fatigue score
- number of prior ITP therapies
- number of types of prior ITP therapies

Baseline disease characteristics will be presented using frequency tabulations for:

- baseline platelet level category
- history of splenectomy
- receiving concurrent ITP therapies at baseline
- history of gastrointestinal bleeding
- number of events of gastrointestinal bleeding
- history of intracranial hemorrhage
- number of events of intracranial hemorrhage
- history of hemorrhage from coagulation disorder
- number of events of hemorrhage from coagulation disorder
- patient with chronic or persistent ITP
- received prior ITP therapy (yes/no), number of prior ITP therapies, number of prior ITP therapies received category (<3, ≥3)
- number of types of prior ITP therapies
- WHO bleeding score
- WHO bleeding score category

All demographic data and baseline disease characteristics will be listed. History of splenectomy, history of gastrointestinal bleeding, history of intracranial hemorrhage and history of hemorrhage of coagulation disorder will be shown on a separate listing specific for ITP history.

3.4 MEDICAL HISTORY AND CONCOMITANT DISEASES

3.4.1 Available data

Medical history findings are coded into system organ classes (SOC) and preferred terms (PTs) using the medical dictionary for regulatory activities (MedDRA), version 24.1. For each finding, a start and stop date or ongoing flag is collected.

SGS	Statistical Analysis Plan	
ARGX-113-1801	Final analysis	Final 1.0 of 28MAR2022

For primary ITP history the following data are collected:

- Date of initial diagnosis
- Date of confirmation per American Society of Hematology (ASH) criteria
- Persistent/chronic ITP

3.4.2 Derivation rules

Medical history finding: not ongoing at screening, ended before date of signing informed consent

Concomitant disease: medical history condition still ongoing at screening

3.4.3 Presentation of results

Prior splenectomy events had to be captured as ITP therapy in the clinical database and will therefore not be shown in the medical history displays.

Medical history and concomitant diseases will be tabulated separately. Both tables will show:

- The number and percentage of patients with findings
- The number and percentage of patients with gastrointestinal bleeding, intracranial hemorrhage and coagulation disorder hemorrhage
- The number and percentage of patients with findings by SOC and PT

For primary ITP history the following data will be tabulated:

• The number and percentage of patients with chronic and persistent ITP.

All medical history, prior vaccinations, primary ITP history, and concomitant disease data will be listed.

3.5 PRIOR AND CONCOMITANT THERAPIES

3.5.1 Available data

All therapies are coded using the September 2021 version of the WHO-DRUG Dictionary. Anatomical therapeutic chemical (ATC) selection is performed. The ATC coding up to level 4 is available in the clinical database. For each therapy, a start date or prior flag and stop date or ongoing flag are collected.

3.5.2 Derivation rules

Based on their start and stop date, therapies will be allocated into 1 or both of the following categories:

- Prior: any therapy that strictly started before the first IMP dose date.
- Concomitant: any therapy that was taken on or after the first IMP dose date.

A medication that started before the first IMP dose date and continued during the study will be classified as both prior and concomitant.

SGS	Statistical Analysis Plan	
ARGX-113-1801	Final analysis	Final 1.0 of 28MAR2022

The ITP-specific therapies will be allocated to the following categories:

- Prior ITP therapy: stopped prior to first IMP dose date
- Continued concurrent ITP therapy: started prior to first IMP dose date and continued after first IMP dose date
- New concurrent ITP therapy: started after first IMP dose date

Therapies with (partially) missing dates will be allocated to each category unless the available parts of the therapy start or stop date or the started prior to trial/ongoing at end of trial flag provide evidence not to do so.

Type of ITP therapy:

- Corticosteroids: selection based on ATC2 = 'H02'
- IVIG, anti-D: selection based on ATC2 = 'J06' or CMDECOD = 'ANTI-D IMMUNOGLOBULIN'
- Thrombopoietin-receptor agonists (TPO-RA): selection based on CMDECOD = ('AVATROMBOPAG MALEATE' or 'AVATROMBOPAG' or 'ELTROMBOPAG' or 'ELTROMBOPAG OLAMINE' or 'ROMIPLOSTIM')
- Fostamatinib: selection based on CMDECOD = ('FOSTAMATINIB' or 'FOSTAMATINIB DISODIUM')
- Other immunosuppressants (azathioprine, cyclophosphamide, cyclosporine A, mophetil mycophenolate, vinca alkaloids): selection based on CMDECOD = ('AZATHIOPRINE' or 'CICLOSPORINE' or 'CYCLOPHOSPHAMIDE' or 'MYCOPHENOLATE MOFETIL' or 'MYCOPHENOLATE SODIUM' or 'SIROLIMUS' or 'VINBLASTINE SULFATE' or 'VINCRISTINE' or 'VINCRISTINE SULFATE')
- Danazol: selection based on ATC4 = 'G03XA'
- Dapsone: selection based on ATC4 = 'J04BA'
- Anti-CD20 (Rituximab): selection based on ATC4 = 'L01XC'
- Other: ITP therapies that are not in any of the previous 9 categories

Rescue ITP therapy will be allocated to the following categories:

- methylprednisolone, dexamethasone, prednisone: selection based on ATC4
 = "H02AB"
- immunoglobulins given IV (IVIg): selection based on ATC4 = "J06BA"
- IV anti-D: selection based on CMDECOD = 'ANTI-D IMMUNOGLOBULIN'
- platelet transfusions: selection based on CMDECOD = 'PLATELETS, CONCENTRATED'
- other: rescue medications that are not in any of the 4 previous categories

Occurrence of rescue therapy: a period of maximum 5 days where 1 or more rescue treatments are administered simultaneously or consecutively to the study patient. The start date/time of the occurrence is the start of the administration of the first rescue treatment. If this period exceeds the maximum of 5 days, a new occurrence will be

SGS	Statistical Analysis Plan	
ARGX-113-1801	Final analysis	Final 1.0 of 28MAR2022

assigned, with start date/time of the occurrence being the start date 5 days after the initial occurrence start date.

More information on the use of rescue therapy can be found in the CTP section 6.8.4.

3.5.3 Presentation of results

Prior and concomitant therapies will be tabulated (separately), by ATC class (level 1 and 3) and generic term.

All prior and concomitant therapies data will be listed with detailed information about ATC classes.

Similarly, prior and concurrent ITP therapy and rescue ITP therapy will be tabulated and listed separately. For splenectomy, the generic term is non-informative ('ALL OTHER NON-THERAPEUTIC PRODUCTS') and therefore the analysis category 'splenectomy' will be shown instead.

Prior ITP therapy and concurrent ITP therapy at baseline will also be tabulated (separately) by type of ITP therapy.

3.6 STUDY DRUG ADMINISTRATION

3.6.1 Available data

For each study drug administration, the start and end date/times, and the volumes will be recorded.

3.6.2 Derivation rules

The following parameters will be derived:

- Number of administrations: sum of all administrations of study drug.
- Compliance (%): 100*(number of doses received/number of doses expected); Compliance will be calculated over the 24-week treatment period and will take into account the weekly or q2w administration.

Notes:

- Dosing is expected at a visit except if reason not done is "DUE TO BIWEEKLY ADMINISTRATION" or "DUE TO PLATELET COUNT > 400X10^9/L"
- Only visits up to treatment discontinuation are considered in the compliance calculation.
- Cumulative duration of q2w dosing: number of weeks for which the patient was on the q2w dosing regimen
- Dosing frequency will be derived for subjects still being dosed at or after visit 17, based on dosing at CRF visits 14, 15, 16 and 17:
 - Biweekly (q2w): if the patient was not dosed at visit 15 or at visit 16
 "DUE TO BIWEEKLY ADMINISTRATION"
 - Else, Weekly: if the patient was dosed at both visit 15 and 16
 Note: in case of missing information at visit 15 and/or 16, a missed visit 15 or 16 is considered as dosed and visits 14 and 17 are also

SGS	Statistical Analysis Plan	
 ARGX-113-1801	Final analysis	Final 1.0 of 28MAR2022

taken into account. If the patient was dosed at two subsequent visits in this timeframe, dosing frequency is set to weekly.

• Else, Unknown: in case dosing frequency cannot be determined based on the above rules.

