### **6.8.4.** Rescue Therapy

"Rescue therapy" is defined as an occurrence where the patient needs treatment with 1 or more rescue treatments. An "occurrence" is defined as a period of maximum 5 days where 1 or more rescue treatments are administered simultaneously or consecutively to the trial patient. The start date/time of the occurrence is the start of the administration of the first rescue treatment.

Rescue therapy is allowed for patients having protocol-defined ITP clinical deterioration AND if in addition the treating physician believes that the patient's health is in jeopardy if rescue therapy is not given.

Rescue therapy is allowed post-baseline during the 24-week trial period for patients with a platelet count of  $<30\times10^9$ /L and 1 of the following:

- an immediate risk of bleeding or a clinically significant bleeding, or wet purpura
- requirement for urgent or emergent surgery (elective surgeries must be postponed until trial completion)

The following rescue therapies are permitted:

- IV methylprednisolone up to 1 g/day  $\times$  1-3 days, oral dexamethasone up to 40 mg/day  $\times$  1-3 days, or oral prednisone up to 1 mg/kg/day  $\times$  1-2 days
- IVIg: up to 1 g/kg/day  $\times$  1-2 days
- IV anti-D: up to 50-75 mcg/kg/day × 1-2 days Note: Anti-D rescue therapy should not be given to Rh(D)-positive patients
- platelet transfusions

If a patient needs rescue therapy according to the investigator, it is encouraged to inform the medical monitor at the sponsor's designated CRO, whenever possible prior to actual implementation of the rescue therapy.

In the event of rescue with IVIg or IV anti-D:

argenx BVBA Confidential Page **63** of **162** 

If given at a visit where the IMP was due to be administered, the IMP should be withheld and administered at the next visit (see also Section 4.5 and Section 6.11).

For rescue therapy with methylprednisolone, dexamethasone, prednisone, or platelet transfusions:

Administration of the IMP continues during rescue therapy

Patients who were receiving q2w dosing at the time of rescue therapy will have the IMP administration frequency increased to weekly.

For patients who receive rescue therapy, the platelet counts for 4 weeks after the first day of the rescue treatment will not be used (ie, are censored) to assess whether or not the patient can transition to q2w treatment.

Patients requiring more than 3 occurrences of rescue therapy will discontinue from IMP.

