### Patients With COVID-19 (Either a Positive Test or With Symptoms)

The instructions to manage infections in the main protocol are also applicable in case of COVID-19 (ie, it will be considered as an AESI). The administration of IMP may be temporarily withheld if, in the opinion of the investigator, it could put the patient at undue risk in circumstances as clinically significant disease, including evidence of infection (see Section 4.5).

[figure not shown]
During the pandemic, site staff or home nurse should call patients prior to each visit to enquire about COVID-19 symptoms, and to check for exposure and infection with the virus before deciding to proceed with the visit using the flow charts below. In case the patient is placed in quarantine and is not able to receive IMP, the investigator can specify in the eCRF that there was no intention to administer IMP due to COVID-19.

For all assessments not performed at the trial site, "COVID-19: home visit" or "COVID-19: phone call" will be added as a comment in the eCRF.

argenx BVBA Confidential Page 103 of 162

Figure 2 Decision Tree for the Treatment of Patients

[figure not shown]
COVID-19 OUTBREAK: IMPACT ON ARGENX STUDIES - SCREENING AND RANDOMIZATION OF PATIENTS

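### The SAP's compliance ratio scores an IMP dose withheld as the protocol directs, because of IVIg or IV anti-D rescue at a due visit, as a dose not received

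*SAP*

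**What the plan says.** SAP 3.6.2 gives the formula: "Compliance (%): 100*(number of doses received/number of doses expected". It then sets the denominator: "Dosing is expected at a visit except if reason not done is" either the biweekly regimen or a platelet count above 400×10⁹/L. No third reason is listed. It adds: "Only visits up to treatment discontinuation are considered in the compliance calculation".

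Where the rescue agent is IVIg or IV anti-D, Protocol 6.8.4 directs the following: "If given at a visit where the IMP was due to be administered, the IMP should be withheld and administered at the next visit". The Synopsis and Section 4.1 repeat the instruction. For rescue with corticosteroids or platelet transfusion it says the opposite: "Administration of the IMP continues during rescue therapy". It also says: "Patients who were receiving q2w dosing at the time of rescue therapy will have the IMP administration frequency increased to weekly". More than three rescue occurrences end IMP treatment.

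Protocol 4.5 requires IMP to be withheld when the platelet count exceeds 400×10⁹/L. It permits withholding for significant disease including infection, for severe bleeding, and for thrombosis. Protocol Appendix 4 adds that, for a quarantined patient who cannot receive IMP, "the investigator can specify in the eCRF that there was no intention to administer IMP due to COVID-19".

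**The concern.** By excusing the hold for counts above 400×10⁹/L, the SAP already accepts that a hold directed by the protocol is not a failure to comply. It does not extend this to the other directed hold, the one for IVIg or IV anti-D rescue. The two holds occur at opposite ends of the outcome: one follows a very high count, while rescue requires a count below 30×10⁹/L. Two patients who both followed the protocol can therefore receive different compliance values because of how their platelets behaved.

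At stake is how Tables 14.1.2.12.1 to 14.1.2.12.3 (safety set, FAS and FAS-chronic) are read. A reader will take compliance there to mean adherence to the regimen. For rescued patients it would partly measure rescue use.

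**Working it through.** The plan states no expected compliance figure, so there is none to reproduce. The check applies the SAP rule to a patient who misses nothing except by protocol direction.

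**Inputs**
- Visits with a possible infusion on the weekly regimen: 24 (visits 1 to 24, Protocol 5.4.1).
- Visits removed from the expected count: biweekly off-visits and holds for counts above 400×10⁹/L (SAP 3.6.2).
- Rescue holds, w: 0 to 3, because a fourth rescue occurrence ends IMP (Protocol 6.8.4).
- Assumption: the site records a rescue hold under a reason other than the two excused ones, since neither describes it.

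**SAP rule, weekly patient:** compliance = 100 × (24 − w) / 24
- w = 0: 24/24 = 100%
- w = 1: 23/24 = 95.8%
- w = 2: 22/24 = 91.7%
- w = 3: 21/24 = 87.5%

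**Same number of holds for counts above 400×10⁹/L:** these leave both counts, so three give 21/21 = 100%.

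**Rescue holds also removed from the expected count:** 23/23, 22/22 and 21/21, each 100%.

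**Does the dose at the next visit make up the loss?** No. A weekly patient already has a dose due at that visit. A q2w patient is moved to weekly dosing, so the next visit adds one to received and one to expected. Either way the ratio stays one dose short.

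**Shorter treatment.** Only visits up to treatment discontinuation count, so each hold weighs more when treatment stops early. A weekly patient whose last counted visit is visit 12, with three holds, scores 9/12 = 75.0%.

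**Between arms.** With 24 weekly visits in both arms and mean holds per patient m, mean compliance is 100 × (24 − m) / 24, and the gap is 100 × (difference in m) / 24. The documents give no rescue rates, so the means below (efgartigimod vs placebo) are assumptions:
- 0.1 vs 0.3: 99.6% vs 98.8%, gap 0.2/24 = 0.8 points
- 0.2 vs 0.5: 99.2% vs 97.9%, gap 0.3/24 = 1.25 points
- 0.3 vs 1.0: 98.8% vs 95.8%, gap 0.7/24 = 2.9 points
- 0.5 vs 0.5: 97.9% in both, no gap

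**The case against.** The strongest reply is that little turns on this. SAP 3.6.3 summarises compliance descriptively. The per-protocol set in SAP 2.1.1 excludes major protocol deviations and uses no compliance cut-off. The number of administrations is tabulated alongside, and rescue is tabulated by category and listed, so a careful reader could separate rescue holds from non-adherence. All of this stands, and it limits the point to a small correction.

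It can also be said that a withheld dose is literally a dose not received, and that Protocol 6.8.4 cross-refers this hold to Section 6.11 on missed doses. That reading is defensible in isolation. But Section 6.11 concerns stopping IMP after more than two consecutive missed doses and does not define compliance. Nor does the reading explain why the hold for counts above 400×10⁹/L is excused.

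Three stronger readings are tempting, and the documents do not support them.
- A reader might infer that compliance will be lower on placebo because rescue should be commoner there. Rescue in general is not the driver: only IVIg or IV anti-D given at a due visit withholds IMP, and no rates by arm, type or timing are given.
- A reader might infer a larger loss for patients mostly on q2w, for example two or three holds among 14 expected doses. Rescue moves a q2w patient to weekly dosing, and platelet counts cannot support a return to q2w for 4 weeks, so a mostly-q2w completer cannot reach that combination while following the protocol.
- A reader might infer that COVID-19 quarantine visits are mis-scored in the same way. The Appendix 4 entry is an optional record, not a directed hold, and the documents do not show how it maps to the recorded reason for not dosing.

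**Conclusion.** The point holds as an inconsistency in the compliance derivation. Under the stated rule, a fully adherent weekly patient with 24 visits scores 95.8%, 91.7% or 87.5% after one, two or three IVIg or IV anti-D holds, against 100% after the same number of holds for counts above 400×10⁹/L. The lowest of these needs all three permitted rescue occurrences to be of this type and each to fall on a dosing visit, so it is an extreme case.

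Any difference between arms is conditional on the arms differing in this rescue at due visits: about 0.8 to 3 points over the assumed range, and none if the rates are equal. The primary and key secondary analyses, the analysis sets and the sample size are unaffected. This is a minor correction worth making because it changes a reported number and is cheap.

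**What to change.** In SAP 3.6.2, add one reason for which dosing is not expected: IMP withheld because of IVIg or IV anti-D rescue at that visit. Show two other groups as separate counts rather than excusing them: visits recorded as no intention to administer IMP because of COVID-19, and the other holds permitted by Protocol 4.5. Keep the planned number of administrations, so that reduced exposure from holds stays visible.

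The cost is one line of text and a small programming change using the recorded reason for not dosing and the rescue dates. Compliance rises slightly, and readers must look to the number of administrations for exposure. No clinical rule changes.
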